## 237 **2. Considerations**

### 238 **2.1 Risks**

239 Safety testing of both the BIOS SkyView lamp and the Aooshine Bedside Lamp was completed via  
240 Underwriter Laboratories. (Document: QOVZ.E516890). Both the SkyView lamp (assessment ID: 109744)  
241 and the Aooshine Bedside Lamp (assessment ID: 133975) have both been approved for IRB study use by  
242 CCHMC.

243 There is a risk associated with wearing CR-39 lenses, as they are not as impact resistant as polycarbonate  
244 (mechanical strength class S vs F, respectively). Parents and participants will be educated on the risk via  
245 the consent form and encouraged to either remove eyeglasses or wear different eyeglasses for activities  
246 where there is a strong risk of impact to eyeglass lenses (i.e. sports). If participants are assigned to study  
247 group 2 (CR-39 lenses throughout the day), parents and participants will be reminded verbally of this risk  
248 using the language present in the consent form.

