#### 170 **4.9 Study Design**

##### 171 **A) Study Groups:**

172 To assess the effects of violet light and potential contribution from UV-blocking glasses, three study  
173 groups will be established:

- 174 1. A group (n = 24) will use the BIOS SkyView lamp with violet LEDs enabled for at least one hour  
175 during dawn and at least one hour during dusk. The group will wear CR-39 (UV-transmitting).
- 176 2. A group (n = 24) will use the BIOS SkyView lamp with violet LEDs enabled for at least one hour  
177 during dawn and at least one hour during dusk. The group will wear polycarbonate (UV-blocking)  
178 glasses for the duration of the study.

179 3. A group (n = 24) will use the Aooshine lamp without any violet LEDs enabled for at least one  
180 hour during dawn and at least one hour during dusk. The group will wear CR-39 (UV-  
181 transmitting).

182 The study lamp (BIOS or Aooshine) should be the sole source of artificial illumination in participant  
183 rooms for the duration of lamp exposure, and throughout the study, exposure to natural light during  
184 designated dawn and dusk times should be minimized. Light is a noninvasive source of therapy, and as  
185 such, tracking the actual exposure to the lamps and compliance to the study design can be difficult.  
186 Therefore, the HOBO Occupancy Sensor (UX90-005), which measures movements of heat emitted by  
187 people in motion via passive infrared technology, will be paired with each BIOS lamp.

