#### 306 **4.4 Sample Size**

307 Up to 72 participants will be enrolled in this study. Up to 24 will be enrolled into the three experimental  
308 groups:

- 309 • Violet light experimental group with polycarbonate glasses

- 310       • Violet light experimental group with CR-39 glasses
- 311       • Non-violet control group with CR-39 glasses.

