#### 364 4.8 Refractive Correction

365 To be eligible for randomization, the participant must be wearing refractive correction in each eye  
366 (single vision eyeglasses or soft, daily wear single vision contact lenses with any necessary  
367 adjustment for contact lens rotation and vertex distance) that meets the following criteria:

- 368 1. Myopia (by spherical equivalent) in both eyes must be corrected to within  $\pm 0.50$  D the  
369 investigator's cycloplegic measurement of refractive error.
- 370 2. Cylinder power in both eyes must be within  $\pm 0.50$  D of the investigator's standard refraction  
371 technique, which can be based on a cycloplegic or non-cycloplegic refraction.
- 372 3. Cylinder axis for both eyes must be within  $\pm 5$  degrees of the axis found on the investigator's  
373 standard refraction when cylinder power is  $\geq 1.00$  D or within  $\pm 15$  degrees when the cylinder  
374 power is  $< 1.00$  D.

375 Measurement of refractive error for assessing the above criteria may be performed as an over  
376 refraction or without refractive correction. If the participant meets all eligibility criteria, but their  
377 current correction does not meet the requirements for randomization, then new refractive  
378 correction (or a change in refractive correction) can be prescribed to meet the requirements. A new  
379 (or change) in refractive correction can also be prescribed if the investigator elects to change a  
380 smaller amount of refractive error, but the resulting prescription must meet the criteria above. The  
381 prescribed correction can be single vision eyeglasses or contact lenses. Single vision lenses will be

382 paid for by the study; contact lenses will be at the participants' own expense. A pair of eyeglasses is  
383 recommended for all participants and may be ordered through Zenni by the study team.

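### Section 2.1 directs the verbal CR-39 impact-risk reminder to study group 2, but the only numbered group list puts group 2 in polycarbonate and groups 1 and 3 in CR-39

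*Protocol*

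**What the plan says.** Section 2.1 (Risks) states that CR-39 is less impact resistant than polycarbonate and provides two layers of communication. The first goes to everyone: families are told of the risk through "the consent form and encouraged to either remove eyeglasses or wear different eyeglasses for activities" with a strong chance of impact to the lenses, such as sports. The second follows assignment and is limited to one group: "group 2 (CR-39 lenses throughout the day), parents and participants will be reminded verbally of this risk". It is to use the language of the consent form.

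The groups are numbered in one place only, Study Design, A) Study Groups (headed 4.9 in the body, 1.7 in the table of contents):

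- Group 1, violet lamp: "during dawn and at least one hour during dusk. The group will wear CR-39 (UV-transmitting"
- Group 2, violet lamp: "during dawn and at least one hour during dusk. The group will wear polycarbonate (UV-blocking"
- Group 3, non-violet lamp: "hour during dawn and at least one hour during dusk. The group will wear CR-39 (UV"

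Sections 4.4 and 5.1 list the same three groups without numbers and in a different order: violet with polycarbonate, then violet with CR-39, then the control. Section 4.4 gives the control entry as "Non-violet control group with CR-39 glasses".

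**The concern.** In section 2.1 the group number and the description in parentheses disagree when read against the numbered list: the number points to the polycarbonate group and the description to CR-39. The sentence also names one group where two wear the lens in question.

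This is an instruction to act on, for children aged 5 to under 13. Consent comes before randomization, so the consent form cannot tell a family which lens their child will receive. In the protocol text, the verbal reminder is the only risk communication that depends on the assigned lens. Neither section 6.1 (glasses pickup) nor section 7.2 (telephone calls) restates it, so nothing elsewhere corrects the label. What is at stake is whether every family of a CR-39 wearer hears the advice repeated.

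**Working it through.** This is a check of a cross-reference plus a count; no power or sample-size formula applies.

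**Inputs**
- Planned total and group size, section 4.4: "Up to 72 participants will be enrolled in this study. Up to 24 will be enrolled into the three experimental" groups. The numbered list gives n = 24 for each group.
- Allocation 1:1:1, section 5.1.
- Lens by group, from the numbered list: group 1 CR-39, group 2 polycarbonate, group 3 CR-39. Sections 4.4 and 5.1 agree that two of the three groups wear CR-39.

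**Reproducing the plan's total:** 3 × 24 = 72, as stated.

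**Children assigned CR-39:** 24 (violet) + 24 (control) = 48 of 72. Polycarbonate: 72 − 48 = 24.

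**CR-39 wearers who miss the reminder = 48 − CR-39 wearers reminded**

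1. *By the number in the numbered list.* The reminder goes to the 24 polycarbonate children. CR-39 wearers reminded: 0. Missed: 48 − 0 = 48.
2. *By position in the unnumbered lists of 4.4 and 5.1.* The second entry is violet with CR-39, so the parenthesis is true for it, but the control group is left out. CR-39 wearers reminded: 24. Missed: 48 − 24 = 24, which is 24/48 = 50% of CR-39 wearers and 24/72 = 33% of participants.
3. *By the parenthesis, applied to anyone given CR-39.* CR-39 wearers reminded: 48. Missed: 48 − 48 = 0.

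**Can any single number be right?** No. Two groups wear CR-39 however the three are numbered, so a condition naming one group covers at most 24 of 48.

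**After the fix** (groups 1 and 3 of the numbered list): reminded 24 + 24 = 48, missed 0.

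All counts are planned maxima. Enrolment may stop short of 72, and section 4.8 lets a child use contact lenses instead: "prescribed correction can be single vision eyeglasses or contact lenses. Single vision lenses will be" paid for by the study. Fewer than 48 children may therefore actually wear CR-39.

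**The case against.** The strongest reply is that the intent is plain. The parenthesis tells staff that the reminder is for children in CR-39, and section 5.1 keeps the study coordinator unmasked precisely so that the right lenses are supplied. A coordinator who sees a CR-39 order can give the reminder whatever the number says, and the gap is then zero. The reminder also repeats consent-form language, so a family that misses it loses a repetition, not information. A protocol need not state an instruction twice, so its absence from section 6.1 is not a fault in itself.

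Most of this stands, and it sets the size of the point. It does not make the sentence correct: the number contradicts the numbered list, and a safety instruction should not depend on staff noticing that.

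A reader might infer more than the protocol supports, in three ways:

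- *That the control group is the one left out.* This treats position in the unnumbered lists of 4.4 and 5.1 as a group number. The one list that has numbers gives a different result, and nothing shows which numbering the author of section 2.1 had in mind.
- *That all 48 CR-39 wearers will go without the reminder.* This follows the number and ignores the description beside it.
- *That some families will not know of the impact risk.* Section 2.1 gives the advice to all families through the consent form.

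**Conclusion.** The inconsistency holds as a labelling error in an operative safety instruction. Section 2.1 describes group 2 as CR-39, the numbered list makes it polycarbonate, and two groups wear CR-39, so no single number is right.

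The number of CR-39 wearers missed is up to 48, up to 24 or 0, depending on whether staff follow the number, the unnumbered order or the parenthesis. The protocol gives no basis for choosing among these, so no one figure should be quoted as the expected gap. The counts assume full enrolment at 24 per group and that every assigned child wears study glasses.

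The consequence is minor. Only the verbal repetition is at risk, and no endpoint, analysis or sample size changes. The contradiction itself is certain because it can be read directly from the text; how many families would be missed in practice is not known.

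**What to change.** In section 2.1, replace the reference to group 2 and its parenthesis with a condition on the lens: *assigned CR-39 lenses (study groups 1 and 3)*. This directs the reminder to all CR-39 wearers, up to 48 of 48, and agrees with the numbered list.

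The cost is one phrase. Section 6 carries no reminder text, so nothing there has to change. The consent form and manual of procedures are not shown; if either repeats the group 2 label, it needs the same correction. Reminding all families would also close the gap, at the price of up to 72 − 48 = 24 reminders to polycarbonate families who do not need them, but resolving the inconsistency does not require it.

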## 218 **1.8 Study Objective**

219 The purpose of this short-term, pilot, randomized trial is to investigate the efficacy of violet light  
220 exposure through the BIOS SkyView Lamps at dawn and dusk versus non-violet light exposure through  
221 Aooshine Bedside Lamps in slowing the progression of myopia in school aged children as an alternative  
222 to current clinical treatments to determine whether to proceed to a full-scale longer-term randomized  
223 trial. This decision will be based primarily on assessing responses to light exposure by comparing  
224 treatment groups on the following outcomes:

- 225 • Axial length elongation
- 226 • Spherical refractive error
- 227 • Quality of life
- 228 • The proportion of participants reporting adverse effects
- 229 • The proportion of participants reporting >75% light exposure compliance

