## 384 **5. Randomization**

### 385 **5.1 Randomization Process**

386 Participants eligible for randomization will be randomly assigned in a 1:1:1 distribution respectively to:

- 387 • Violet light experimental group (BIOS SkyView Lamp) with polycarbonate glasses
- 388 • Violet light experimental group (BIOS SkyView Lamp) with CR-39 glasses
- 389 • Non-violet control group (Aooshine Bedside Lamp) with CR-39 glasses

390 The investigator will construct a separate Master Randomization List using a permuted block design  
391 stratified by the treatment group. A participant is considered randomized when REDCap randomization  
392 process is completed.

393 The participant, parents, testers, and investigators will be masked to treatment group. If the need arises,  
394 the investigator may become unmasked after discussion of a specific case with the study team in  
395 response to any adverse events. The study coordinator will remain unmasked to the treatment group in  
396 order to facilitate the type of equipment and lenses the participant will need.

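### The assignment-dependent CR-39 reminder in section 2.1 gives masked families information about their arm, contrary to section 5.1, and it is unclear which families receive it

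*Protocol*

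**What the plan says.** Section 2.1 describes two steps. The first applies to everyone: "Parents and participants will be educated on the risk via" the consent form, with advice about activities where the lenses might be struck. The second depends on assignment. If the child is assigned to "group 2 (CR-39 lenses throughout the day"), then "parents and participants will be reminded verbally of this risk", in the consent-form language.

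Section 5.1 states: "The participant, parents, testers, and investigators will be masked to treatment group". One role is routinely exempt: "The study coordinator will remain unmasked to the treatment group in" order to arrange the right equipment and lenses. Children are "randomly assigned in a 1:1:1 distribution respectively to" three arms, each a lamp paired with a lens: violet with polycarbonate, violet with CR-39, and non-violet with CR-39.

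The Study Groups list (printed as 4.9 A, listed as 1.7 (A) in the table of contents) numbers the arms. Its item 2 is a violet-lamp arm whose entry reads in part "during dawn and at least one hour during dusk. The group will wear polycarbonate (UV-blocking"). Items 1 and 3 are the CR-39 arms. Group 2 is therefore CR-39 in section 2.1 and polycarbonate in the Study Groups list.

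**The concern.** Treatment group in 5.1 means lamp and lens together, and nothing in the protocol limits masking to the lamp. A spoken CR-39 warning, given because of the child's assignment, tells a masked family something about the lens. Sections 2.1 and 5.1 cannot both be followed as written. This is a matter of trial conduct, not a detail that a statistical analysis plan would settle.

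The lens also carries information about the lamp, because the two are not crossed: polycarbonate never occurs with the control lamp.

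What is at stake is data that families report or control. Section 1.8 bases the decision on a full-scale trial on five outcomes, among them "The proportion of participants reporting adverse effects" and light-exposure compliance. Parents report lamp use every day (7.1), and adverse effects are elicited by questioning (7.3, 9.3). Families also decide whether the child stays in the room with the lamp and how far natural light is kept down at dawn and dusk. A belief about the arm could affect any of these.

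**Working it through.** **Inputs.** Three arms of 24 (Study Groups list; 4.4), allocated 1:1:1 (5.1). Total 3 × 24 = 72, which reproduces the stated enrolment. Violet arms: 24 + 24 = 48. CR-39 arms: 24 + 24 = 48. Polycarbonate arm: 24, all violet.

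**Before any reminder.** P(violet) = 48/72 = 2/3.

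**Formula.** P(violet | reminder status) = violet families with that status ÷ all families with that status. It assumes that the family knows the three-arm design and which arm or arms are reminded.

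| Who is reminded | P(violet), reminded | P(violet), not reminded |
|---|---|---|
| A. Both CR-39 arms (the risk described) | 24/48 = 1/2 | 24/24 = 1 |
| B. Violet CR-39 arm only | 24/24 = 1 | 24/48 = 1/2 |
| C. Polycarbonate arm (the number in the Study Groups list) | 24/24 = 1 | 24/48 = 1/2 |

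Reading B has some support in the text: the unnumbered lists in 4.4 and 5.1 put violet with CR-39 second. Under B, the control arm, which also wears CR-39, would get no spoken reminder. Under C, the reminder would go to the one arm that does not wear CR-39.

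**What each figure needs.** Under A, the 48 reminded families learn their lens directly. They reach 1/2 if they know how lens and lamp are paired. The other 24 reach 1 only if they infer polycarbonate from silence. Under B, a reminded family that knows only that it has CR-39 is at 24/48 = 1/2. It reaches 1 only if it knows that this arm alone is reminded.

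**Overall leak.** Under each reading one violet arm is at 1 and the other two arms are at 1/2. Mean belief in violet is (1 + 1/2)/2 = 75% across the two violet arms and 50% in the control arm. Entropy about the lamp falls from 0.918 bits to (48/72) × 1 + (24/72) × 0 = 0.667 bits, a loss of 1 − 0.667/0.918 = 27%. The rate of correct best guesses does not change. It is 48/72 before the reminder and (24 + 24)/72 = 48/72 after it. The leak makes 24 families certain; it does not make the average family a better guesser.

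**After the change.** If all 72 families hear the same reminder, it carries no information and P(violet) stays at 2/3.

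**The case against.** The strongest reply has four parts.

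- **The size is not fixed by the text.** Section 2.1 names one group of 24, so a statement that 48 families are told their lens assumes more than it says. This stands, and it is why the figures are given by reading. Some assignment information leaks under every reading.
- **Inference from silence is assumed.** Every family already gets the CR-39 risk through consent, and the protocol nowhere says that families learn who else is reminded. A reader might infer that polycarbonate families will know their lamp with certainty. The documents do not support that; it is a worst case. Section 4.2 requires parents to understand the protocol, which makes knowledge of the three arms plausible but does not establish it. Disclosure of the lens to a reminded CR-39 family needs no such inference.
- **The lamp may already be recognisable.** The violet and control lamps are different branded products, set up and kept at home, and the protocol describes no concealment. Section 2.5 also mentions polycarbonate upgrades, which could bring up the lens. This stands: changing 2.1 alone would not secure lamp masking. It does not excuse a procedure that itself discloses the lens.
- **The main endpoints are objective.** A reader might infer that the primary analysis is biased by this sentence. The documents do not show that. Cycloplegic autorefraction and optical biometry are instrument measurements, and the reminder does not directly unmask testers. Compliance has a sensor record beside the parent survey. Quality of life is named in 1.8 but appears in neither the visit schedule nor 7.3. Section 9.1 compares violet with non-violet light and names no separate lens comparison. Any effect on refraction would have to act through family behaviour, for which the protocol gives no figure.

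**Conclusion.** The point holds in a limited form. Section 2.1 makes a reminder depend on assignment, and 5.1 masks the people who receive it to groups that include the lens. The contradiction is in the text and does not depend on how the group number is resolved.

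The effect on lamp belief is at most 24 families moving from 2/3 to 1 and 48 moving from 2/3 to 1/2. It rests on the 1:1:1 allocation of 72, on families knowing the three-arm design, and on their knowing or inferring who is reminded. The protocol does not establish the last two, and the conflict over group 2 leaves open which families are affected.

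The exposure lies mainly in the daily lamp-use survey, reported adverse effects and behaviour at home. It should be corrected because it is cheap to correct, not because it invalidates the primary comparison.

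**What to change.** Reconcile section 2.1, the Study Groups list and section 5.1. In 2.1, replace the assignment-dependent sentence with one verbal reminder, in the consent-form language, given to all families after randomization by the unmasked coordinator and without linking it to the child's assignment. This also removes the need for a group number in that sentence.

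If the sponsor prefers a lens-specific warning for safety, 5.1 should instead state that families are not masked to lens type, and 2.1 should identify the arm or arms concerned by lens and lamp, consistently with the Study Groups list.

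The cost of the common reminder is one sentence and a shared script. Polycarbonate families (24 at full enrolment) hear a caution they do not need, and the warning to the 48 CR-39 families becomes less specific. It does not address whether the two lamp brands can be told apart, which is a separate threat to masking.

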### 249 **2.2 Risk of Examination Procedures**

250 The procedures in this study are part of daily eye care practice in the United States and pose no known  
251 risks.

### 252 **2.3 Risk Assessment**

253 It is the investigator's opinion that the protocol's level of risk falls under DHHS 46.404, which is research  
254 not involving greater than minimal risk.

255

256 **2.4 Reporting of Adverse Events**

257 There are no expected long-term adverse events associated with violet light exposure. The investigator  
258 will abide by CCHMC IRB reporting requirements.

259 **2.5 Study Costs**

260 This study will be funded internally through CCHMC RIP grant. The department of ophthalmology will be  
261 the final dispenser of funds.

262 The subject or his/her insurance provider will be responsible for the costs that are considered standard  
263 of care. Because the treatment used in the study is not standard of care, the Enrollment/Randomization,  
264 Equipment Pickup and 2 Follow-Up visits will be paid for by the study. The cost of the SkyView/Aooshine  
265 lamp will also be paid for by the study. For subjects who wear prescription lenses and are assigned to a  
266 group that requires CR-39 or polycarbonate lenses to be worn, the study will provide spectacles and  
267 lenses from Zenni Optical not to exceed \$80 subject to the following:

- 268 • If the patient/parent desires more expensive frames, they will be responsible for costs that  
269 exceed \$80.
- 270 • Lens add-ons and upgrades are at study participant’s own expense (e.g., transition lenses,  
271 premium polycarbonate lenses).

272 **3. Study Outline**

	Enrollment/Randomization	Visit 2: Equipment Recieval	6-Month Visit	12- Month Visit
	Day ≤0	Week 4 ± 2 weeks	6 Months ± 2 weeks	12 Months ± 2 weeks
Informed Consent	X			
Demographics	X			
Medical History	X		X	X
Standard Refraction	X		X	X
Cycloplegic Autorefraction	X		X	X
Distance Visual Acuity Testing	X		X	X
Binocular Near Visual Acuity	X		X	X
Monocular Amplitude of Accomodation	X		X	X
Axial Length Measurement	X*	X*		X**
OCTA	X*	X*		X**
Prescribe Refractive Correction If Needed	X		X	
Randomization	X			
Receive Lamp		X		
Receive Glasses		X		
Receive HOBO Sensor		X		
Receive Automated Wall Plug-In		X		
HOBO Sensor Data Collection			X	X

273

274 \*Only required if not able to complete at Enrollment/Randomization Visit.

275 \*\* Testing may occur at a separate testing visit if testing equipment is unavailable at the 12-Month Visit. This must  
276 occur ± 2 weeks of the 12- Month Visit.

277 **4. Enrollment**

278 **4.1 Eligibility Assessment**

279 A child is considered for the study after undergoing a routine eye examination (as part of standard care)  
280 where myopia is identified, and the child appears to meet the eligibility criteria for enrollment. The  
281 study will be discussed with the child's guardian(s). Guardians who express an interest in the study will  
282 be given a copy of the informed consent form to read. Written informed consent must be obtained from  
283 the guardians prior to performing any study-specific procedures that are not part of routine care.

284 Participants aged 5 to <13 years with myopia who meet all eligibility criteria will be enrolled in the study.  
285 Up to 72 participants will be enrolled and randomized in the study.

